Examination of reading skills (method by L.A. Fotekova, T.V. Akhutina, 2002)	+		+
Examination of spelling skills (method by L.A. Fotekova, T.V. Akhutina, 2002)	+		+
Examination of counting skills ("Arithmetic" subtest No. 3 of WISC)	+		+
Inclusion/exclusion criteria	+		
Randomization and prescription of study therapy	+		
Study drug supply	+		
Study drug accountability, compliance assessment			+
Distribution of diaries	+		
Evaluation of correct diary filling			+
Diary return			+
CGI-EI scale filling			+
Evaluation of treatment safety	+	+	+

Statistical Analyses

Samples

Total set includes all the subjects who have signed ICF. This sample will consider all adverse events throughout the study, including those occurred prior to the study therapy.

The sample including all subjects who received at least one dose of the study product to be used for ***analysis of the study treatment safety and tolerability*** (*Safety population*), as all adverse events identified after the study product administration will be recorded.

Full Analysis Set This sample will consist of all enrolled subjects, except for those who met at least one of the following criteria:

- 1) failure to meet inclusion/non-inclusion criteria;
- 2) subject failing to take any dose of the study drug;
- 3) absence of any data on the subject after randomization.

This was the best set for the Intention-to-treat method, so it will be used in the ***Intention-to-treat efficacy analysis of the test therapy***.

Per Protocol set. This sample includes all subjects who completed the therapy as per the study protocol, without any missing visits or major protocol deviations. This set will be used in the ***Per Protocol efficacy analysis of the test therapy***.

Mean value of the total set for the relevant day will be used to fill lacking/missing data.

Data treatment and all statistical calculations under the protocol will be made using SAS-9.3 statistical software.³

Evaluation of sample size

The sample size was assessed in accordance with the following rules and assumptions:

1. Statistical assumptions:

- 1.1 the power of statistical tests is 80% (the probability of correct rejection of the null hypothesis is 0.8)
- 1.2 the probability of type 1 error ' α ' is less than 0.05 (the probability of false acceptance of the alternative hypothesis)
- 1.3 statistical criteria used are two-sided

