- 1.4 value of clinically relevant " δ " difference is taken as equal to 5 (i.e. Tenoten for children effect is supposed to be clinically relevant compared to placebo effect if the effect in the study group exceeds the one in control group by at least 5 points)
- 1.5 statistical null and alternative hypotheses will be as follows:

³ Holder of license: OOO "NPF "MATERIA MEDICA HOLDING", No. 70100045.

$$H_0: m_1 - m_2 \leq \delta$$

$$H_1: m_1 - m_2 > \delta,$$

where m_1 - mean total scholastic skill score in Tenoten for children group

m_2 – mean total scholastic skill score in placebo group

δ – clinically relevant difference value.

1.6 an interim analysis is planned for potential adjustment of sample size:

- a. calculations will be made using O'Brien-Fleming boundary;
- b. proportions of the subjects completing the study and yielding the results for interim and final analyses, will be taken as 0.5 and 1.0 (i.e. interim analysis will be made after recruitment of half of the planned number of the clinical study subjects).

1.7 therefore, sample size will be calculated taking into account:

- a. interim analysis;
- b. assumption on expected effects declared in the main efficacy criterion of the protocol.

1.8 calculation of sample size in groups 1 and 2 for two-sided test for interim and final analysis will be made using the formula defining sample size (i.e. for the variant without interim analysis):

$$N_1 = N_2 = (\sigma_1^2 + \sigma_2^2) I,$$

where N_1 and N_2 are sample sizes in Tenoten for children and placebo groups

σ_1 and σ_2 – expected standard deviations in these groups

I – Fisher information determined using the formula:

$$I = (F^{-1}(1-\alpha) + F^{-1}(1-\beta))^2 / \theta_1^2,$$

where $F^{-1}(1-\alpha)$ and $F^{-1}(1-\beta)$ are tabular z-test values for α and β , a $\theta_1 = (m_1 - m_2)$.

1.9 final sample size will be determined using the formula:

$$N_F = N_{PP} / (1 - C_w),$$

where N_F – final sample size;

N_{PP} – result of calculation in cl. 1.8, i.e. scheduled number of subjects

completing the study per protocol;

C_w – withdrawal coefficient.

2. Assumptions on expected clinical study effects:

The difference between Tenoten for children effect consisting in increased mean total scholastic skill score by the end of therapy and effect in placebo group is supposed to be at least 10 points with standard deviation of at least 12 points.

Given the statistical terms and assumptions above each group size will be:

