- a) at interim analysis - 46 subjects
- b) at final analysis - 92 subjects.

Therefore, total PP set will include 184 subjects.

Taking into account that potential withdrawal of 30% subjects at the screening and during the study for various reasons, at least **132** subjects in each group will be required to sign informed consent (in total **264** subjects).

Statistical criteria

All statistical calculations will be made using two groups of statistical criteria:

- parametric - to evaluate continuous and interval random values;
- nonparametric – to obtain:
 - evaluations of equality/inequality of proportions of the subjects upon their comparison for various visits,
 - analysis of frequencies of the features compared,and
 - evaluation of continuous and interval random values in case of non-compliance with normal random distribution.

The following SAS procedures are suggested for interim analysis:

- SEQDESIGN, SEQTEST – design and performance of interim analysis;
- The terms of early termination of the study will be set using O'Brien-Fleming stopping boundary.

Parametric criteria

Prior to analysis using parametric statistics, data samples under comparison will be tested for normality (the Kolmogorov-Smirnov test).

The following parameters and approaches are to be used:

1. To evaluate the differences in continuous variables from two different (independent) groups – Student's test for independent samples.
2. To evaluate differences in continuous variables in one group at two different visits - Student's test for paired samples.
3. To evaluate time changes in parameters compared - analysis of variance (ANOVA) or modified repeated measures covariance (ANCOVA).
4. In case of multiple comparisons of the groups various corrections for multiplicity will be used, e.g. Dunnett, Tukey, Scheffe, Holm adapted test, etc.
5. Generalized Linear Models will be used in case of abnormal data distribution.

6. Selection of the type of distribution, specification of factor and covariance structures of the model will be made using fit-statistics such as AIC (Akaike information criterion).

The following SAS software programs are supposed to be applied to the above listed tests and techniques:

- UNIVARIATE: normality verification of the distributions under comparison;
- CORR, MEANS - calculation of descriptive statistics
- TTEST – Student's test with all modifications
- GLM – generalized linear models for analysis of time changes (ANOVA, ANCOVA)

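### The hypotheses and the printed sample-size formula are one-sided, the text says two-sided, and no critical value is given: two-sided 0.05 is the better-supported reading, but a one-sided 0.05 threshold is not ruled out

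*Combined protocol and SAP*

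**What the plan says.** All the relevant text is in the Statistical Analyses part of the combined protocol and SAP.

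- **Evaluation of sample size, item 1.2:** the type 1 error "is less than 0.05 (the probability of false acceptance of the alternative hypothesis". The item does not mention sidedness.
- **Item 1.3:** "statistical criteria used are two-sided".
- **Item 1.4:** the clinically relevant "difference is taken as equal to 5" points.
- **Item 1.5:** the null is that the Tenoten minus placebo difference is at most delta. The alternative is "H_1: m_1 - m_2 > \delta".
- **Item 1.8, words:** the calculation "for two-sided test for interim and final analysis will be made using the formula defining sample size".
- **Item 1.8, formula:** "I = (F^{-1}(1-\alpha) + F^{-1}(1-\beta))^2", divided by the squared difference in means. The alpha quantile is taken at 1-alpha, not 1-alpha/2.
- **Statistical criteria:** "The terms of early termination of the study will be set using O'Brien-Fleming stopping boundary". The summary's Interim analysis paragraph and item 1.6 instead give the purpose of the interim as possible sample-size adjustment.

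The stated result is 46 per group at the interim and 92 at the final analysis. No critical value, p-value threshold or success rule is given for either look.

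**The concern.** The plan gives two signals about the tail area used to declare success. A directional alternative with alpha defined as the chance of falsely accepting it, together with a formula that uses the 1-alpha quantile, can be read as a one-sided test at 0.05. The statements in items 1.3 and 1.8 put 0.025 in the direction that favours Tenoten.

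An O'Brien-Fleming boundary cannot be computed until alpha and sidedness are fixed, so the ambiguity carries into the SEQDESIGN input, the final threshold and any early-stopping threshold. A borderline result would succeed under one reading and fail under the other, and either could be defended from the text after unblinding. The printed quantile carries a second risk: item 1.8 is the formula an analyst would take up again for the interim sample-size adjustment.

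**Working it through.** **Inputs.** Power 80% (item 1.1); alpha 0.05 (item 1.2); delta 5 (item 1.4); expected difference 10 and SD 12 (assumptions on expected effects, where both are minimum values); equal allocation; O'Brien-Fleming with looks at information 0.5 and 1.0 (item 1.6).

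**Step 1: reproduce 92.** Per group, n = 2 × SD² × (z_alpha + z_beta)² / d². With d = 10 - 5 = 5, the multiplier is 2 × 144 / 25 = 11.52.

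- Upper tail 0.025: 11.52 × (1.960 + 0.842)² = 90.42. The two-look O'Brien-Fleming factor of 1.0078 gives 91.12, rounded up to **92**; half is 46. This matches the plan.
- Upper tail 0.05, the quantile as printed: 11.52 × (1.645 + 0.842)² = 71.22. The factor of 1.0156 gives 72.34, rounded up to **73**.
- With d = 10, the fixed-design values are 22.6 (upper tail 0.025) and 17.8 (upper tail 0.05), so the 5-point distance is needed in either case.

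A fixed-design t-test calculation also gives 92 for two-sided 0.05 (91.4) and 72 for one-sided 0.05 (71.9). The inference about the tail area therefore does not depend on the O'Brien-Fleming factor.

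**Step 2: boundaries.** Two-look O'Brien-Fleming boundaries have the form c√2 at the interim and c at the final look. They were solved from the bivariate normal distribution with correlation √0.5. The standard error of the difference is 12√(2/46) = 2.502 at the interim and 12√(2/92) = 1.769 at the final analysis. The observed difference needed is 5 + z × SE.

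| | Two-sided 0.05 | One-sided 0.05 |
|---|---|---|
| Interim z | 2.797 | 2.373 |
| Interim difference, points | 12.00 | 10.94 |
| Final z | 1.977 | 1.678 |
| Final difference, points | 8.50 | 7.97 |
| False acceptance of H1 at the null boundary | 0.025 | 0.050 |
| Power at a true difference of 10, 92 per group | 80.4% | 87.7% |
| Interim crossing at a true difference of 10 | 21% | 35% |

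The rejection regions are nested, so about 87.7 - 80.4 = 7% of trials at the design alternative would change verdict. A Lan-DeMets O'Brien-Fleming-type spending function shows the same pattern: 2.96 against 2.54 at the interim and 1.97 against 1.66 at the final look.

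**Step 3: reusing the printed quantile.** 1 - 71.22/90.42 = 0.21, so re-estimating with 1-alpha would undersize the trial by about 21%. If 72 per group were then tested at two-sided 0.05, fixed-design power would be Φ(5 / (12√(2/72)) - 1.96) = Φ(0.54), about 71% rather than 80%.

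**Step 4: does this depend on the margin?** With a null of 0 the final thresholds are 1.977 × 1.769 = 3.5 points and 1.678 × 1.769 = 3.0 points. The gap of about half a point remains.

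**The case against.** The strongest reply is that the plan is two-sided and only loosely worded. Sidedness is stated twice, once explicitly for both looks, and 92 per group cannot be obtained any other way from the plan's inputs. This stands, and it decides which reading to keep. It does not remove the directional hypothesis, the 1-alpha quantile or the missing critical value.

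Three stronger readings are tempting but not supported.

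- **That items 1.2 and 1.3 contradict each other.** Item 1.2 sets a ceiling, not an equality. An upper tail of 0.025 is below 0.05, so the two are compatible. Item 1.2 alone does not define a one-sided 0.05 test.
- **That a literal two-sided rule would pass a useless drug.** With a true difference of zero and a null of 5, the statistic crosses the lower boundary in about 80% of trials. Nothing in the plan treats a result significantly below delta as success, so this is not a false-positive rate.
- **That the looser reading doubles the false-positive rate for an ineffective drug under the stated null.** The doubling applies at a true benefit of exactly 5 points. With the null at 5, a zero-effect drug would win with probability about 0.000009 against 0.000002. Doubling for an ineffective drug arises only if the null is 0.

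The interim contrast also matters only if the boundary is used to stop for efficacy. The Statistical criteria text points that way, while the stated purpose of the interim is sample-size adjustment.

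**Conclusion.** The concern holds as an unresolved inconsistency in the decision rule, with two-sided 0.05 clearly the better-supported reading. The sample size is not wrong under that reading.

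The exposure is a borderline result. With SD 12, 92 per group and a null of 5, observed differences between 7.97 and 8.50 points at the final look would succeed only under one-sided 0.05. At the interim the range is 10.94 to 12.00 points, if efficacy stopping applies. Both ranges widen in proportion to the SD, which the plan gives as a minimum. The doubling of false acceptance at the null boundary, from 0.025 to 0.050, holds at any SD. The undersizing of about 21% arises only if item 1.8 is applied as printed at the sample-size adjustment.

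The point is worth correcting before any unblinded look, because the success threshold of a phase III trial should not be open to choice.

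**What to change.** Make items 1.2, 1.3, 1.5 and 1.8 say the same thing:

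- The primary test is at two-sided 0.05, equivalently one-sided 0.025.
- Success is declared only if the statistic exceeds the upper O'Brien-Fleming boundary: z > 2.797 at information 0.5 (if the interim may stop for efficacy) and z > 1.977 at the final analysis.
- A lower-tail crossing is never acceptance of H1.
- In item 1.8, replace F⁻¹(1-alpha) with F⁻¹(1-alpha/2), so that the formula agrees with its own description and with the quantile behind 92, and use that form in any sample-size adjustment.
- Enter the same alpha and sidedness in SEQDESIGN.

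Item 1.8 must be changed together with the others. Otherwise it would keep a quantile that does not reproduce 92.

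The cost is wording in four items and one program setting. The 92 per group is unchanged, and all that is given up is a laxer one-sided 0.05 threshold that the sizing did not use.

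### The printed sample-size formula (item 1.8) leaves out the 5-point margin and gives 23 per group, not the stated 92; the SD is given only as a floor

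*Combined protocol and SAP*

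**What the plan says.** All references are to the section Evaluation of sample size.

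- Items 1.1 to 1.3 set 80% power, alpha 0.05 and two-sided tests.
- Item 1.4 sets the clinically relevant difference delta at 5 points, and item 1.5 builds it into the null hypothesis: "H_0: m_1 - m_2 \leq \delta".
- Item 1.6 plans an interim analysis at half the subjects for a possible change of sample size, and says that "calculations will be made using O'Brien-Fleming boundary". Item 1.7 lists the interim analysis among the things for which "sample size will be calculated taking into account".
- Item 1.8 covers the "calculation of sample size in groups 1 and 2 for two-sided test". The per-group size is the sum of the two variances times I, where "I = (F^{-1}(1-\alpha) + F^{-1}(1-\beta))^2 / \theta_1^2" and theta1 is defined as m1 - m2. Delta does not appear. The item says that the calculation "for interim and final analysis will be made using the formula defining sample size (i.e. for the variant without interim analysis").
- Item 1.9 defines N_PP as the "result of calculation in cl. 1.8, i.e. scheduled number of subjects" completing per protocol, and divides it by one minus the withdrawal coefficient.
- Part 2 gives the effect assumption: the difference "is supposed to be at least 10 points with standard deviation of at least 12 points".
- The results are 46 per group at the interim, 92 per group at the end (184 in total), and 132 per group (264) after 30% withdrawal.

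**The concern.** The plan states one hypothesis and prints a formula for another. Item 1.5 asks whether the drug beats placebo by more than 5 points. Item 1.8 sizes a trial to show a difference from zero. Because the size varies with the inverse square of the effect, replacing 5 by 10 changes it by a factor of four. The printed rule and the stated 92 cannot both be right.

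Two things are at stake. First, item 1.8 is the only formula printed for the per-group size, and it is said to serve the interim as well as the final analysis. Anyone who recalculates the size at the interim under item 1.6 would naturally turn to it. Second, power against a margin depends heavily on the SD. Part 2 bounds the SD from below, which is the favourable end, so the 80% in item 1.1 is tied to the smallest SD that the plan allows.

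**Working it through.** **Inputs.** Power 80% (item 1.1, z = 0.842); alpha 0.05, two-sided (items 1.2 and 1.3, z = 1.960; z = 1.645 if the printed 1-alpha is taken as 0.95); delta 5 (item 1.4); difference 10 and SD 12 in both groups (part 2); looks at 0.5 and 1.0 with an O'Brien-Fleming boundary (item 1.6); withdrawal 30%. I assume that the directional hypothesis of item 1.5 is tested with the two-sided 0.05 critical value, that is, 0.025 in the upper tail.

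**Reproducing the stated figure.** Put theta1 = 10 - 5 = 5 and use the 1-alpha/2 quantile:

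- (144 + 144) x (1.960 + 0.842)^2 / 5^2 = 90.4 per group.
- Route A: multiply by the two-look O'Brien-Fleming inflation of 1.0078 (bounds 2.797 and 1.977). This gives 91.1, so 92, and 46 at the interim.
- Route B: a fixed-design two-sample t-test with the same inputs has power 79.8% at 91 and 80.3% at 92 per group, so also 92.
- Withdrawal: 92 / 0.7 = 131.4, so 132 per group and 264 in total, as stated.

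A 5-point difference against a zero null is the same arithmetic and also gives 92.

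**Item 1.8 as printed**, with theta1 = m1 - m2 = 10:

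- With 1-alpha/2: 288 x (1.960 + 0.842)^2 / 10^2 = 22.6, so 23 per group.
- With 1-alpha = 0.95: 288 x (1.645 + 0.842)^2 / 10^2 = 17.8, so 18 per group.

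O'Brien-Fleming inflation does not close the gap: 22.6 becomes 22.8, and 17.8 becomes 18.1 with the factor of 1.0156 that applies at 0.05 in one tail.

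**Where the gap comes from.** 17.81 x 4 (effect 5 instead of 10) = 71.2; x 1.2695 (quantile) = 90.4; x 1.0078 (inflation) = 91.1. The margin is the main cause. The conflict between the no-interim label in item 1.8 and the interim allowance in item 1.7 is worth about one subject per group. The ratio of needed to printed size is 91/23 = 4.0, or 91/18 = 5.1.

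**Power of 92 per group under the two-look design.** SDs above 12 and differences above 10 are illustrative, since the documents give no upper value for either.

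| Null | True difference | SD: power |
|---|---|---|
| margin 5 | 10 | 12: 80%; 13: 74%; 14: 67%; 15: 61% |
| margin 5 | 11 | 13: 87.7%; 14: 82.5%; 14.4: 80.4% |
| margin 5 | 12 | 16: 84.0% |
| zero | 10 | 15: 99%; 18: 96%; 24: 80% |

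At a true difference of 10, power reaches 80% at an SD of 12.06 against the margin and 24.12 against zero.

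**The case against.** The strongest reply is that nothing operational is wrong. The plan states 92, 132 and 264 outright, and these agree with its own hypotheses. That stands. A reader might carry the printed formula through item 1.9 and conclude that the trial should enrol, or risks enrolling, a fraction of 264; the documents do not support this, because the enrolment figure is stated directly. A reader might equally infer that 264 is a miscalculation, and it is not.

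The quantile deserves a charitable reading. Items 1.3 and 1.8 both say two-sided, so alpha in the formula may be meant per tail. The fair figure is then 23 and not 18. This also stands, but it leaves the margin missing.

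It is tempting to say that the O'Brien-Fleming inflation is how 92 was obtained. The documents do not settle this: the fixed-design t-test gives 92 too, and it fits the no-interim wording of item 1.8.

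On the SD, 12 is the value that reproduces 92, so it already acts as the planning value. The difference of 10 is also a floor, in the favourable direction, and a larger true difference would offset a larger SD. The interim adjustment could deal with a larger SD as well, although no re-estimation rule is printed. If the test is in fact against zero (Parametric criteria names Student's test and mentions no margin), the SD concern largely goes away. So it cannot be said that the trial is underpowered, only that the 80% is conditional in a way that part 2 does not state.

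Finally, the document calls itself a protocol summary, so a fuller derivation may exist elsewhere. The inconsistency within this text remains.

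**Conclusion.** The point holds as a fault in the written rule, and it should be fixed. Item 1.8 contradicts item 1.5 and gives 23 per group (18 on the literal quantile) where the plan states 92. The stated sizes are consistent with the margin hypothesis at SD 12 and two-sided alpha 0.05, and they can stay. Item 1.5 favours that reading, but the documents do not exclude a 5-point difference against zero.

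This is more than notation, because item 1.8 is tied to the interim analysis and item 1.6 foresees a change of sample size there. Applied as printed, the rule would understate the size needed for the item 1.5 hypothesis four- to five-fold. That consequence assumes that an adjustment would use item 1.8, the only per-group formula given.

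The SD floor is a second, lesser point. It rests on the margin null and a true difference of 10, and under those conditions 80% power holds only at the bottom of the stated SD range.

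**What to change.** - **Item 1.8:** define theta1 as (m1 - m2) - delta = 10 - 5 = 5, print F^-1(1-alpha/2), and state that this version applies to any interim sample-size adjustment.
- **Route to 92:** the sponsor should state the step actually used from 90.4 to 92 (O'Brien-Fleming inflation or t-test), bring the no-interim label in item 1.8 into line with item 1.7, and confirm that the margin null of item 1.5 is the hypothesis to be tested.
- **Part 2:** replace the SD floor with a planning standard deviation of 12 points. State that 80% power against the margin is conditional on that SD and a true difference of at least 10, and give power at larger SDs (74%, 67% and 61% at 13, 14 and 15 for a difference of 10).
- **Keep** 92, 132 and 264.

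The cost is a change of text only. The downside is that the power statement becomes openly conditional on the SD and the true difference.

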**Multicenter double-blind placebo-controlled randomized
clinical trial of efficacy and safety of Tenoten for children in
the treatment of specific developmental disorders of
scholastic skills in children**

Phase III

Sponsor	ООО «NPF «MATERIA MEDICA HOLDING»
Protocol number	MMH-TD-005
Version date:	January 22, 2015
ClinicalTrials.gov Id:	NCT03159104

Protocol Summary

This document represents the protocol summary for the study on human subjects. The study will be carried out in accordance with ICH GCP, National Standard of the Russian Federation GOST 52379-2005 "Good Clinical Practice", Helsinki Declaration of World Medical Association, relevant requirements of the regulatory authorities as well as the study procedures.

Title of Study

Multicenter double-blind placebo-controlled randomized clinical trial of efficacy and safety of Tenoten for children in the treatment of specific developmental disorders of scholastic skills in children.

Phase: III

Sponsor: OOO «NPF «MATERIA MEDICA HOLDING», Moscow, Russia

Protocol No. MMH-TN-005

Objective of the study

- To evaluate efficacy and safety of Tenoten for children in the treatment of specific developmental disorders of scholastic skills in children.

Endpoints

Primary endpoint

1. Mean total scholastic skill score (reading, spelling and counting) in the groups after 12-week therapy compared to baseline.

Secondary endpoints

1. Mean score of "Reading skill test" in the groups after 12-week therapy compared to baseline.
2. Mean score of "Spelling skill test" in the groups after 12-week therapy compared to baseline.
3. Mean score of subtest No. 3 "Arithmetic" (of Wechsler Intelligence Scale for Children, WISC) in the groups after 12-week therapy compared to baseline.
4. Percentage of children with an increase in total scholastic skill score¹ (reading, spelling and counting) in the groups after 12-week therapy compared to baseline.
5. Efficacy Index according to Clinical Global Impression scaly by the end of therapy (CGI-EI).

¹ Improvement criterion – increased total scholastic skill score (reading, spelling and counting) by at least 5 points compared to baseline.

Safety assessment

- Occurrence and nature of adverse events (AE) during the treatment; AE severity, causal relationship to the study drug, and outcome.

Study design

A multicenter, double-blind, randomized, placebo-controlled clinical trial to evaluate the efficacy and safety of the study treatment.

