At Visit 3 (Week 12±3 days) repeated testing of reading, spelling and counting skills will be made, complaints, data on concomitant diseases, concomitant therapy, and adverse events will be collected. The investigator will evaluate the subject's compliance and fill in the Clinical Global Impression Scale to calculate Efficacy Index (CGI-EI).

The patients will be allowed to take symptomatic therapy and medications for their co-morbidities during the study, except for the medicines listed in "Forbidden concomitant therapy".

Inclusion and exclusion criteria

Inclusion criteria

1. Children of either gender aged 7 to 9 years old.
2. School children of grades 1-3 (grade 1 children will be enrolled at the beginning of the second half of the year) in regular schools with state accreditation with principal educational program of elementary general education in compliance with Federal State Educational Standard of the Russian Federation.
3. Beginning of the second half of the year (only for 1st grades).
4. Specific developmental disorder of scholastic skills such as:
 - specific reading disorder (F81.0);
 - specific spelling disorder (F81.1);
 - specific disorder of arithmetical skills (F81.2);
 - mixed disorder of scholastic skills (F81.3; i.e. meeting the criteria for one of the following combinations: F81.2+F81.0, F81.2+F81.1, or F81.2+F81.0+F81.1).
5. Reading score of 15 to 35 on the Reading Skills test (L.A. Fotekova, T.V. Akhutina, 2002).
6. Spelling score of 15 to 30 on the Spelling Skills test (L.A. Fotekova, T.V. Akhutina, 2002).
7. Counting score of 5 to 15 on the subtest No. 3 "Arithmetic" (of Wechsler Intelligence Scale for Children).
8. Availability of a patient information sheet (Informed Consent Form) signed by the parent/adopter to confirm the child's participation in the clinical trial.

Exclusion criteria

1. History of the diseases:
 - Diseases of the nervous system, including:
 - inflammatory diseases of the central nervous system,
 - systemic atrophies,
 - extrapyramidal and movement disorders,
 - degenerative diseases of the nervous system,

- demyelinating diseases of the central nervous system,
- episodic and paroxysmal disorders,
- polyneuropathies,
- diseases of myoneural junction and muscle,
- cerebral palsy.
- Congenital malformations of the nervous system (excl. Spina bifida without hydrocephalus).
- Diseases and congenital malformations of eye causing impairment of vision.

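### The protocol summary assigns no test to the primary endpoint; one baseline-adjusted ANCOVA should be prespecified, the same at interim and final analysis

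*Combined protocol and SAP*

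**What the plan says.** The primary endpoint (Endpoints) is "Mean total scholastic skill score (reading, spelling and counting) in the groups after 12-week therapy compared to baseline". No test is named there.

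Evaluation of sample size, item 1.4, calls the effect relevant "if the effect in the study group exceeds the one in control group by at least 5 points". Item 1.5 tests H0: m1 - m2 ≤ 5 and defines m1 only as "mean total scholastic skill score in Tenoten for children group", with neither visit nor change stated. Item 2 describes the expected effect as "increased mean total scholastic skill score by the end of therapy and effect in placebo group is supposed to be at least 10 points", with an SD of at least 12.

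Statistical criteria is organised by variable type, not by endpoint:

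- The parametric methods open with a gate: "Prior to analysis using parametric statistics, data samples under comparison will be tested for normality (the Kolmogorov-Smirnov test").
- Parametric item 1 gives Student's test for two independent groups.
- Parametric item 3 reads "To evaluate time changes in parameters compared - analysis of variance (ANOVA) or modified repeated measures covariance (ANCOVA"). No covariate is named.
- Parametric item 5 sends non-normal data to generalized linear models. Item 6 lets AIC select the distribution and the factor and covariance structures.
- Non-parametric item 1 gives Mann-Whitney for two independent groups.

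For the interim look, "The terms of early termination of the study will be set using" an O'Brien-Fleming boundary, using SEQDESIGN and SEQTEST. The statistic to be supplied to them is not named.

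**The concern.** An endpoint expressed against baseline fits item 1 (t-test on change) and item 3 (time changes by ANOVA or ANCOVA) about equally well. If normality fails, two fallbacks compete and no rule decides between them. Two analysts following this text could report different primary results from the same data.

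The same gap reaches the interim look. A group-sequential boundary controls error for one defined statistic computed the same way at each look. At stake are the primary conclusion and a stopping decision. Power is also at stake, to a smaller extent, because the implied default does not adjust for a baseline score that is already collected.

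**Working it through.** **1. The plan's own sample size.** Inputs from Evaluation of sample size: expected difference 10, margin 5, SD 12, two-sided 0.05, power 80%, O'Brien-Fleming at information 0.5 and 1.0, withdrawal 30%.

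- Fixed sample: n = 2 × 12² × (1.960 + 0.842)² / (10 - 5)² = 90.4, so 91 per group.
- The two-look O'Brien-Fleming boundaries are z = 2.797 (p about 0.0052) and z = 1.977 (p about 0.048). They raise n to 91.1, so 92 per group, with 46 at the interim.
- Withdrawal: 92 / 0.70 = 131.4, so 132 per group and 264 in total.

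The stated figures are reproduced. They correspond to an unadjusted comparison of two means against the 5-point margin.

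**2. Assumptions the documents do not supply.** SD 12 is taken as the SD of change. The correlation rho between baseline and Week 12 is taken as 0.3 to 0.7. For the baseline SD I use inclusion criteria 5 to 7, starting with "Reading score of 15 to 35 on the Reading Skills test", then spelling 15 to 30 and arithmetic 5 to 15. If they apply jointly and scores are uniform within each range:

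- independent scores: √((20² + 15² + 10²)/12) = 7.8
- perfectly correlated scores: 45/√12 = 13.0

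**3. ANCOVA residual SD.** The Week-12 SD (sw) solves 12² = sb² + sw² - 2·rho·sb·sw (larger root), where sb is the baseline SD. The ANCOVA SD is sw·√(1 - rho²). With sb in {7.8, 9, 10, 11, 12, 13}, rho in {0.3, 0.4, 0.5, 0.6, 0.7} and sw not below sb, 23 settings remain.

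**4. Power.** This is noncentral-t, 92 per group, 5 points beyond the margin, two-sided 0.05. For the change t-test the noncentrality is 5/(12·√(2/92)) = 2.83, giving 80.3%. Interim crossing (46 per group, p 0.0052) is 20.1%. For ANCOVA:

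| sb | rho | sw | ANCOVA SD | Final power | Interim crossing |
|---|---|---|---|---|---|
| 10 | 0.3 | 10.28 | 9.81 | 93.1% | 34.4% |
| 12 | 0.5 | 12.00 | 10.39 | 90.1% | 29.5% |
| 7.8 | 0.4 | 12.76 | 11.69 | 82.2% | 21.5% |
| 9 | 0.6 | 15.00 | 12.00 | 80.3% | 20.1% |

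Over all 23 settings ANCOVA power is 80.3 to 93.1%, with median 82.2%; 15 settings are below 84%. At the final O'Brien-Fleming level of 0.048 the comparison is 79.8% against 79.8 to 92.8%.

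The gain depends on the regression slope rho·sw/sb. In the last row it is 0.6 × 15/9 = 1.0, so ANCOVA coincides with the change analysis. In the first row it is 0.3 × 10.28/10 = 0.31, and the gain is large.

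**5. Disagreement between the two tests.** I simulated bivariate normal scores over the same grid, with 10,000 trials per setting.

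- Opposite final verdicts at true difference 10: about 1 to 15% of trials.
- Disagreement on crossing the interim boundary: about 2 to 20%.
- At least one test significant at true difference 5 (two-sided 0.05): about 5 to 8%.

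**The case against.** A default can be read out of the plan. Items 1.5 to 1.8 of the sizing describe a difference of two means with z-values for interim and final analysis. Parametric item 1 names Student's test, and the endpoint wording with items 1.4 and 2 points to change. Item 6 may apply only within generalized linear models, and item 3 may not concern the between-group comparison at all. This stands as far as it goes: the boundary statistic can be inferred. It is still not declared, and items 3 and 5 and non-parametric item 1 leave other routes open.

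A prespecified t-test on change would also remove the ambiguity, so choosing ANCOVA is a preference for efficiency. That is correct, and the typical gain is small. Neither rho nor the baseline SD is in the documents, and uniform scores are only an assumption.

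The text supplied is a protocol summary, so a fuller statistical section might name the test. The point is limited to what is supplied.

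Three stronger readings are tempting and are not supported:

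- A reader might infer that type I error is inflated to about 8%. That is the upper end for picking the better of two tests, and the plan states no such rule. A fixed normality-then-test sequence would not by itself inflate error.
- A reader might count Mann-Whitney among the competing analyses in the simulation. The simulated data are normal, and the plan's Kolmogorov-Smirnov gate would seldom send such data to Mann-Whitney. No figure here includes it.
- A reader might take 90% or more as the power ANCOVA would deliver. That needs similar baseline and Week-12 SDs and a low correlation.

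**Conclusion.** The point holds: the supplied summary assigns no test to the primary endpoint, and the statistic behind the stopping boundary is inferable but not fixed. If SD 12 is the SD of change and the assumed ranges apply, ANCOVA has 80 to 93% power against 80% for the change t-test. The typical gain is about 2 points. On normal data the choice between these two tests reverses the final verdict in about 1 to 15% of trials.

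The main reason to act is the open choice, which remains even where ANCOVA adds no power. ANCOVA is preferred because it is never materially less powerful in these settings. This should be corrected, but it does not show that the trial is underpowered or its error rate uncontrolled: 92 per group remains sufficient under these assumptions.

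**What to change.** Name one primary analysis, identical at interim and final: ANCOVA of the Week-12 total score on treatment and baseline total score. Define m1 - m2 in item 1.5 as that adjusted difference and test it against the 5-point margin. Report its confidence interval at the O'Brien-Fleming-adjusted level, about 95.2% at the final look (1 - 0.048).

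State that neither the Kolmogorov-Smirnov test nor AIC chooses the primary analysis. Keep the t-test on change, Mann-Whitney and generalized linear models as sensitivity analyses.

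The cost is SAP wording and one degree of freedom; the baseline scores are already collected at Visit 1. The change does not settle which analysis set is primary or how missing data are handled.
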